RBS = HIV Risk Behavior Survey; CES-D = Center for Epidemiologic Studies Depression Scale; DTCQ-8 = Drug-Taking Confidence Questionnaire, 8 item version; EQ-5D = EuroQol 5D-5L; PCBSS = Primary Care Buprenorphine Satisfaction Scale; SOCRATES = The Stages of Change Readiness and Treatment Eagerness Scale

Questionnaires: Using the survey feature on REDcap which plays an audio recording of questions as it displays the question on a computer screen, will be used by the RA to administer questionnaires. Interviews will assess for sociodemographic information, motivation for treatment, HIV risk behaviors, buprenorphine diversion, and other variables (see below). Interviews will last 45-60 minutes.

Electronic medication adherence monitors: Wisepill electronic monitors will be used allowing us to monitor if and when medication is taken. Participants will receive a prescription for buprenorphine. After receiving the prescription, research staff will supervise the patient as they place their medication into the Wisepill Medication adherence monitors. Each time the device is opened it sends a signal to a password protected database.

Fidelity of referral: The SEP staff will follow identical procedures for referral or transfer of care to a CHC. We will not be able to blind participants or staff to study allocation. Therefore, we will record the number of appointments and reminder phone calls performed in each arm to ensure that SEP staff members are not providing differential effort in facilitating referral to a CHC.

Main outcome variables: *Aim 1: Primary outcome (efficacy):* we will use a dichotomous measure (yes/no) of **BMT engagement** defined as having an active buprenorphine prescription at 30 days after randomization.³⁰ Secondary outcome measures assessed at 24 weeks will include: proportion who filled a prescription for BMT, total weeks prescribed BMT, and time to BMT initiation (all continuous measures).

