Aim 2: Primary outcome (safety): We will use a dichotomous measure (yes/no) of **buprenorphine diversion** for all participants to determine how many sell or give away prescribed medication. We will define diversion as having at least one problem behavior over the 24 weeks: non-adherence to prescribed medication on electronic monitoring, self-reported diversion, or a urine sample consistent with diversion. Adherence will be determined weekly with Wisepill adherence for one week equaling $X/7Y$, where X = number of openings in one week and Y = number of doses prescribed per day. For the composite measure, non-adherence will be considered < 90% adherence. We will adapt the MGH Medication Questionnaire, which assesses misuse of prescribed medications, including selling medication, letting others take prescribed medication, or taking medication to get “high”. For the composite measure, self-reported diversion will be defined as an affirmative response to the question, “In the past 2 weeks, have you sold your buprenorphine to others?” We will also test each urine sample for buprenorphine, and if absent among participants prescribed BMT, the urine sample will be considered consistent with diversion. Each behavior will also be explored individually.

Aim 2: Secondary outcomes (safety): We will also report illicit buprenorphine use (i.e., buprenorphine detected in urine samples of participants who are not prescribed BMT), and determine changes in illicit buprenorphine use from baseline to study completion among participants in each study arm.

Aim 3: Primary outcome (incremental cost-effectiveness ratio, ICER): The ICER will be calculated by dividing the incremental mean cost of the O-BMT arm relative to the control arm by the incremental mean effectiveness of the O-BMT arm relative to the control arm (instruments used to measure costs and effectiveness are described in detail below). The primary economic effectiveness outcome will be the quality-adjusted life-year (QALY), a measure that incorporates both duration and health-related quality-of-life and is recommended as the primary economic effectiveness measure.⁹⁴ The QALY captures a wider range of consequences than other clinical effectiveness measures, and permits comparisons across disorders and interventions, allowing for broader economic interpretation. Also, generally accepted value thresholds have been established for QALYs, but not for clinical measures.⁹⁵

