Electronic adherence data: Wisepill electronic adherence monitors will be used allowing us to monitor if and when medication is taken. Electronic signal is sent to a password protected database when the device is opened and this data will be used to calculate adherence (or non-adherence) to prescribed medication. Adherence data will be downloaded and saved on a password protected computer.

Vulnerable population. SEP participants with OUD could be vulnerable to undue influence, because of physical dependence to opioids and challenges engaging in BMT. We will also be collecting sensitive information on diversion of buprenorphine, which is a controlled substance. In the following sections, we discuss the risks of enrolling SEP participants and procedures to minimize these risks.

Potential risks. The primary risks of this study are: (1) breach of confidentiality leading to embarrassment, dismissal from SEP, or legal consequences; (2) inconvenience and discomfort associated with interviews; (3) fear that refusal to participate will affect care at the SEP; (4) diversion of prescribed BMT; (5) induced withdrawal after initiating BMT; (6) polysubstance use

Confidentiality issues: We will collect personal information from participants to facilitate tracking, and we will be asking personal questions including substance use and HIV risk behaviors. We have outlined our procedures to maintain confidentiality below.

Inconvenience and discomfort associated with interviews: Participants will be asked about substance use and opioid use disorder treatment. It is possible that such questions could produce anxiety in participants. Participants will be instructed that they may withdraw from the study if this occurs. [name] (a board-certified general internist) will be involved with all study activities and will assess for severe discomfort or other severe community health center or emergency department.

Fear that refusal to participate will affect care or services: Participants may use services at the SEP, such as housing assistance or mental health counseling. In the informed consent process, they will be clearly instructed that refusal to participate will in no way affect their care at the affiliated SEP.

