Diversion of prescribed BMT: For the first two weeks after initiating treatment, prescribed buprenorphine will be provided in electronic adherence monitors to monitor adherence. This should dissuade diversion of buprenorphine. However, if participants do sell or give away their medication, there could be legal consequences or disciplinary action at the SEP. After initiating BMT, participants will be asked about whether they divert their medication, and we will also check urine drug tests with the expectation that participants who are prescribed buprenorphine will have detectable buprenorphine in their urine.

Induced withdrawal after initiating BMT: Participants will start taking their medication at home, so they are subject to induced withdrawal if they take the buprenorphine before fully experiencing opioid withdrawal. This could include diarrhea, nausea, vomiting, musculoskeletal pain, sweating, and anxiety. Standard protocols for home inductions will be followed with similar procedures in the O-BMT and enhanced referral arms. The risk of induced withdrawal will not be increased from routine clinical practice.

Principal Investigator: [name]

Polysubstance use: Though buprenorphine has pharmacologic properties that make it safer than other opioid agonists (e.g., ceiling effect, partial agonist, co-formulation with naloxone), it does lead to some sedation, and overdoses are possible if taken with other sedating substances. If SEP participants are using multiple illicit substances, initiating BMT could add to their risk of overdose.

Adequacy of protection against risks

Recruitment and informed consent: We will obtain informed consent for all participants of the RCT prior to collecting any information with personal identifiers (e.g. locator form or medical record release forms), administering the baseline REDcap interview, and randomization to an intervention arm. Informed consent will be obtained by the RA.

Protection against risk: We will institute the following processes to ensure confidentiality is maintained:

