Appendix 1.

CHCC BUPRENORPHINE MAINTENANCE TREATMENT (BMT) PROTOCOL

1. Intake

- a. On the first visit, gather the H&P w attention to the substance use history, set expectations, check LFTs and utox
- b. Use smart phrase to gather complete substance use history
- c. Use smart phrase to generate BMT Patient Agreement

2. Induction

- a. Second visit, the patient will receive Bupe induction instructions and COW scale.
 - i. Tips: Start with 8 mg tabs/films and ask patient to break in 1/2 or even 1/4. Also prescribe clonidine, loperamide, and ibuprofen for withdrawal symptoms.
 - ii. Induction can be done at home or in the office
 1. Home induction has been tolerated and successful at CHCC

3. Induction and Stabilization

- a. See the patient for follow-up in 1 week, then again 1-2 weeks later until the patient is on a stable dose
- b. Doses can be adjusted based on symptoms of withdrawal and cravings. Sometimes this can be challenging as anxiety can mimic withdrawal symptoms.
- c. Total daily dose: The usual dose is 16 mg total daily (the vast majority range between 8-24mg daily) and doses can be increased by 4 mg/day.
- d. Frequency: Can be dosed daily or bid, adjust according to symptoms, often pts like to split their doses, which is fine

4. Maintenance

- a. Once dose is stable, can space out visits to monthly
- b. Check urine drug testing at every follow-up visit
- c. Assess for use of other substances (cocaine, alcohol, benzodiazepines, etc.) at each follow-up visit
- d. Adopt an uniform approach about cocaine, alcohol, or benzodiazepine use
 - i. Refer to social worker for psychosocial counseling
 - ii. Counsel all patients to minimize use of alcohol, benzodiazepines, and other sedatives
 - iii. Refer to an opioid treatment program if polysubstance use makes risks of continuing buprenorphine treatment greater than benefits

5. Discharge from Treatment

- a. If patients are hostile to staff or adulterate urine they will be given an administrative warning. These expectations should be made clear from day 1.
- b. Repeat offenders should be discharged from the practice and referred to an opioid treatment program

6. Lost to Follow Up:

- a. Track patients who have ever been evaluated for Bupe at your clinic, and periodically review with program coordinator and community outreach worker about outreach/retention efforts for loss to follow up patients.

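### The adherence score X/7Y counts every device opening, so extra openings can mask missed days in the Aim 2 diversion outcome

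*Combined protocol and SAP*

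**What the plan says.** Under Main outcome variables, Aim 2: Primary outcome (safety), a participant is scored as diverting on "having at least one problem behavior over the 24 weeks". One of the three qualifying behaviors is non-adherence on the electronic monitor. Weekly adherence is X/7Y, "where X = number of openings in one week and Y = number of doses prescribed per day", and "non-adherence will be considered < 90% adherence".

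Under Electronic medication adherence monitors, "Each time the device is opened it sends a signal to a password protected database", and at the start "research staff will supervise the patient as they place their medication into the Wisepill Medication adherence monitors". Under Electronic adherence data in the human-subjects part, "this data will be used to calculate adherence (or non-adherence) to prescribed medication". Neither section says that any opening is left out.

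Monitoring covers the first two weeks of treatment in both arms (Assessment of buprenorphine diversion). Loading and the home start therefore both fall in or next to the scored period. Appendix 1 allows once- or twice-daily dosing, has patients break units into halves or quarters at induction, and adds: "often pts like to split their doses, which is fine".

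**The concern.** The formula treats one opening as one prescribed dose, but the plan describes openings that are not whole prescribed doses: loading the device, and possibly part-doses taken at separate times. X is a weekly total, so a surplus on one day cancels a shortfall on another. Because the rule looks only for scores below 90%, surplus openings push a participant towards being called adherent.

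The monitor is the only one of the three diversion components that follows dosing day by day. If it misses gaps, the Aim 2 primary outcome depends on spot urine tests and self-report to find them. The power section presents the frequency of diversion in the O-BMT arm as important safety data in its own right, so the rate matters whether or not H4 can be settled. The plan also sets an interim limit of 30% on aggregate diversion. It does not say whether the same composite is used there; if it is, the same error enters.

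**Working it through.** **Inputs**
- Score X/(7Y), flagged if below 90%; one flagged week is enough (Aim 2 primary outcome).
- Two scored weeks (Assessment of buprenorphine diversion). In the O-BMT arm each onsite visit yields a one-week prescription (Initiation), so one loading per week is plausible. That is an assumption; the plan does not state the number of loadings.
- The number of openings on the start day is not given; three is assumed below.

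The plan gives no worked value for the score, so there is no figure to reproduce.

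**Step 1: where the cut-off falls.** At Y = 1, 7/7 = 100% passes and 6/7 = 85.7% is flagged. At Y = 2, 13/14 = 92.9% passes and 12/14 = 85.7% is flagged. For a once-daily prescription, a single opening decides the result.

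**Step 2: dosing patterns under the written rule and under a capped rule.** The capped rule counts at most Y openings per day, excludes loading, and starts the week at the first non-loading opening.

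| Pattern in one week | As written | Result | Capped rule | Result |
|---|---|---|---|---|
| Y=1, loading + 7 doses | 8/7 = 114.3% | pass | 7/7 = 100% | pass |
| Y=1, loading + 6 doses | 7/7 = 100% | pass | 6/7 = 85.7% | flag |
| Y=1, loading + 5 doses | 6/7 = 85.7% | flag | 5/7 = 71.4% | flag |
| Y=1, dose split in two on all 7 days | 14/7 = 200% | pass | 7/7 = 100% | pass |
| Y=1, two openings on 4 days, none on 3 | 8/7 = 114.3% | pass | 4/7 = 57.1% | flag |
| Y=1, 3 openings on start day, 1 on each of 4 days, 2 days missed | 7/7 = 100% | pass | 5/7 = 71.4% | flag |
| Y=2, day's amount taken at one opening, all 7 days | 7/14 = 50% | flag | 7/14 = 50% | flag |
| Y=1, week counted from loading, first dose 2 days later, none missed | 5/7 = 71.4%, or 6/7 = 85.7% with loading counted | flag | 7/7 = 100% | pass |

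The second, fifth and sixth rows are missed days scored as adherent. The first and fourth show that extra openings do not harm a fully adherent participant. The last two are the only false flags. Merging twice-daily doses on two days is enough for a flag (12/14 = 85.7%); on one day it is not (13/14 = 92.9%).

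**Step 3: how much one extra opening moves the flag rate.** Assume Y = 1 and independent doses, each opened with probability p. The chance of at least one flagged week in two is 1 − P(week passes)².
- p = 0.95, no extra opening: P(pass) = 0.95^7 = 0.698, so 51.2% are flagged.
- p = 0.95, one extra opening each week: P(pass) = 0.95^7 + 7 × 0.05 × 0.95^6 = 0.956, so 8.7% are flagged.
- p = 0.90: 77.1% falls to 27.7%.

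The values of p are illustrative. They show that whether loading is counted is not a detail.

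**The case against.** **Several points stand.**
- The rule is one-sided, so splitting, a stepwise start and loading never flag a fully adherent participant. A reader might infer that all these patterns produce wrong diversion scores. They do not: they inflate the percentage, and change the yes/no result only when doses were also missed.
- Masking by splitting needs Y = 1. If the split dose is prescribed twice daily, the four-day pattern gives 8/14 = 57.1% and is flagged.
- The plan does not say that loading counts in X; it only fails to exclude it.
- Both false-flag cases need facts that the plan does not give. Nothing describes twice-daily patients taking the day's amount at one opening, and someone who does so departs from the prescribed frequency. The plan ties monitoring to the first weeks of treatment, which may mean from the first dose. The warning that participants who start at home "they are subject to induced withdrawal if they take the buprenorphine before fully experiencing opioid withdrawal" is a reason to wait, but gives no length of delay.
- Urine tests and self-report may catch some masked cases.

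**Two further stronger readings are not supported.** One is that false flags could use up the 5-point H4 margin: with 49% against 16% starting treatment, a 15% false-flag rate would add 0.15 × 0.33 = 5.0 points. The 15% has no source, and the 49% and 16% are transfer and enrollment figures from the power section, not start rates. The sum also ignores masking, which lowers observed diversion. The other is that the error differs by arm because splitting appears only in the CHC document. The Control section has CHC providers follow the same initiation procedures as O-BMT.

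**Planned checks do not remove the problem.** The preliminary range check could notice 114%, but not a masked week that scores exactly 100%, and no rule says what to do with either. It is also true that the margin is out of reach at equal observed rates: with 125 per arm and 10–25% diversion, the Wald 95% half-width is 1.96 × √(2p(1−p)/125) = 7.4 to 10.7 points. That limits the effect on the H4 decision, not on the reported rate.

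**Conclusion.** The concern holds as a gap in the outcome definition. With no daily cap and no excluded openings, X/7Y can score a participant as adherent who missed one day (if loading counts) or three days (two openings on each of the other four, Y = 1). False flags are possible, but only if Y stays at 2 while doses are merged, or if the week runs from loading and the first dose is late; the plan should close both openings. How often any of these patterns occurs is not in the documents, and the errors run in opposite directions, so no net shift in the H4 risk difference can be stated. The rule should be corrected before the monitor data are scored.

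**What to change.** Amend the Aim 2 definition as follows.
1. Replace X with the sum over days of min(openings that day, Y), so that extra openings on one day cannot offset another. State the hour at which a day begins.
2. Log the time of each supervised loading and exclude those signals.
3. Start the week at the first non-loading opening, and count in the denominator only days on which the dispensed supply should last. Score a loaded device that is never opened as 0%.
4. Set Y from the prescription in force on each day.
5. Report days covered (days with at least one opening) as a sensitivity analysis for merged twice-daily doses; the merged row in the table then reads 7/7 = 100%. It should not be the primary measure, because a twice-daily participant who opens once a day and diverts the rest would also score 100%.

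The cost is a short program and a loading-time log; opening signals and prescription fill dates are already collected. The downside is a slightly stricter score, so more participants may be flagged, for example when a dose slips past the day boundary. No dosing rule changes.

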Concerns about buprenorphine diversion are common, but data are lacking. Diversion, meaning that patients who are prescribed buprenorphine (including buprenorphine-naloxone) give or sell the medication to others who are not engaged in treatment is a major concern for prescribers and policy makers.⁴⁷⁻⁵⁰ Those taking diverted medication may be “self-treating” withdrawal symptoms, which is common among PWID, or seeking euphoric effects.^{48,51-56} Buprenorphine-naloxone is more commonly prescribed than buprenorphine alone, because the naloxone may reduce abuse potential.⁵⁷ Buprenorphine is a partial opioid agonist that is unlikely to cause euphoria among individuals with high levels of opioid tolerance when taken sublingually. However, it can be adulterated and injected for euphoric effects. The naloxone in the combination product is unabsorbed when taken sublingually, but it is more bioavailable if injected and will provide antagonism at opioid receptors.⁵⁸ Therefore, PWID are unlikely to seek diverted buprenorphine-naloxone to inject for euphoric effect; however, they could divert medication to others posing a public health risk.^{48,51,59} Making BMT available at SEPs, where there is active drug use, could increase risk of diversion; however, it could also address an unmet need for treatment. In 2013, we found that among 102 SEP participants, 57 had taken diverted buprenorphine, and this was most common among those with barriers to BMT.¹³ In focus groups, SEP participants directly reported that they took diverted buprenorphine due to insufficient access to BMT.⁵ Other studies have found inadequate BMT access as a risk factor for using diverted buprenorphine.^{51,60} *Therefore, onsite BMT at SEPs could also paradoxically reduce diversion.* There are also other important areas that require inquiry. Though 35-100% of BMT patients initiating treatment have reported taking diverted buprenorphine, estimates of how many BMT patients divert their own medication to illicit markets are limited.^{56,59,61,62} Among inmates enrolled in trials of BMT initiation prior to jail or prison release, 10-20% were removed from the trials for attempting to divert their medication;^{28,29} however, data relevant to community BMT patients are needed to inform clinical practice and policies regarding buprenorphine prescribing (e.g., establishing monitoring guidelines).

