Rationale for 2 week intervention. The goal of this intervention is to encourage BMT engagement, which we expect to increase from initiating pharmacotherapy. Drop out from BMT is most pronounced in the first week of treatment, but SEP staff will be available for psychosocial support throughout this time.^{75,79} Starting treatment at home does not increase dropout from treatment.^{67,77} After BMT initiation, linkage from community-based settings to primary care is feasible.⁸⁰ We considered continuing BMT onsite for longer than two weeks to accommodate participants who are comfortable with SEP staff but uncomfortable in traditional medical settings;^{3,4} however, there are potential benefits to transferring care. Maintaining BMT at SEPs could expose participants to cues of drug use, which may trigger opioid craving;⁸¹ transfer to a CHC may improve access to medical services (mental health counseling, HIV treatment, etc.);⁸² and segregating care of PWID outside of the traditional health care system risks entrenching “separate and unequal” care.³³

Assessment of buprenorphine diversion. We will assess buprenorphine diversion in three ways. For the first two weeks of treatment in both study arms, electronic monitors will be used enabling us to monitor medication adherence in real time. Participants will be incentivized to return electronic monitors, thereby strengthening the assertion that they did not sell or give away an entire pack. We will ask participants directly about selling their buprenorphine through sequential surveys. Audio computer-assisted self-interview technology through REDcap (see below) may reduce social desirability bias in reporting stigmatized behaviors, and prior studies of medical marijuana diversion have detected high rates of diversion through self-report.⁸³⁻⁸⁵ Additionally, all participants will have urine samples tested to confirm presence of prescribed buprenorphine.

Control: Enhanced referral to BMT. The control condition will be enhanced referral to a CHC for initiation of BMT and maintenance treatment. Similar to O-BMT, the research staff will facilitate linkage to care.

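### The Aim 2 diversion composite does not score admitted giving away, although it is meant to count it; secondarily, its monitor cut-off makes one missed once-daily dose count as diversion

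*Combined protocol and SAP*

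**What the plan says.** Under Main outcome variables, the Aim 2 primary (safety) outcome is a yes/no measure meant "to determine how many sell or give away prescribed medication". The Background describes diversion in the same terms: patients who "give or sell the medication to others who are not engaged in treatment".

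Any one of three components over the 24 weeks makes a participant a diverter.

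- **Self-report.** The adapted questionnaire covers misuse "including selling medication, letting others take prescribed medication". For the composite, only a yes to "In the past 2 weeks, have you sold your buprenorphine to others" counts.
- **Monitor.** The section on assessing diversion limits its use: "For the first two weeks of treatment in both study arms, electronic monitors will be used". It records openings: "Each time the device is opened it sends a signal to a password protected database". Weekly adherence is X/7Y, "where X = number of openings in one week and Y = number of doses prescribed per day". The cut-off follows: "For the composite measure, non-adherence will be considered < 90% adherence".
- **Urine.** A sample without buprenorphine from someone prescribed it counts as consistent with diversion.

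The plan adds that each behaviour will also be looked at individually. H4 is tested on the composite by intention to treat, with a 5% non-inferiority margin.

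**The concern.** The stated purpose covers two behaviours and the self-report rule scores one. The questionnaire lists selling and letting others take medication as separate items, so the sold question cannot be read as including gifts. Someone who openly reports giving doses away is not counted on that report.

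The monitor component raises the opposite worry. It can label an ordinary lapse as diversion, and for a once-daily prescription it allows no lapse at all.

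The definition matters more here than the H4 test alone would suggest. The power section concedes 80% power only at a margin of 10-14%. It then relies on a good estimate of how often diversion occurs in the O-BMT arm as the safety result. That frequency is what the scoring rules determine.

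**Working it through.** **1. Who is scored.** The three component rules can be applied to participants who answer the questionnaire honestly.

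| Behaviour | Sold item | Monitor, weeks 1-2 | Urine | Composite |
|---|---|---|---|---|
| Sells, and says so | yes | either | either | counted |
| Gives away, and openings fall below 90% | no | flagged | either | counted, through the monitor |
| Gives away everything, opens on time, takes none | no | passes | negative if tested while prescribed | counted, through urine |
| Gives away part, opens on time, takes the rest | no | passes | can be positive | can be missed |

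In the last row the participant has admitted the behaviour that the outcome is meant to count. After the first two weeks of treatment there is no monitor, so only the sold item and urine remain. Adding the give-away item can only leave the composite rate unchanged or raise it. By how much cannot be computed, because the documents give no rate of giving away.

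**2. The monitor cut-off.** The plan's figure here is a definition (below 90%), so it can only be evaluated. Appendix 1, item 3d, allows daily or twice-daily dosing. The section on onsite initiation states no frequency.

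| Openings missed in a week | Once daily (Y = 1) | Twice daily (Y = 2) |
|---|---|---|
| 0 | 7/7 = 100%, passes | 14/14 = 100%, passes |
| 1 | 6/7 = 85.7%, flagged | 13/14 = 92.9%, passes |
| 2 | 5/7 = 71.4%, flagged | 12/14 = 85.7%, flagged |

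For a once-daily prescription the nominal 90% is in effect 100%.

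**3. Illustrative size.** Let p be the chance that a scheduled dose is opened. The documents give no value, so p is assumed. Assume also independent misses, two monitored weeks, no diversion and no extra openings.

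- Once daily, P(flag) = 1 − p^14. At p = 0.99 this is 1 − 0.8687 = 0.131. At p = 0.98 it is 1 − 0.7536 = 0.246.
- Twice daily, the weekly pass probability is s = p^14 + 14(1 − p)p^13, and P(flag) = 1 − s². At p = 0.99, s = 0.8687 + 0.1229 = 0.9916 and P(flag) = 0.017. At p = 0.98, s = 0.969 and P(flag) = 0.061.

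These are shares of prescribed participants. The expected diversion rate of 10-25% in the power section is stated for the full intention-to-treat sample, so the two are not directly comparable.

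Relaxing the assumptions lowers the once-daily figures of 13.1% and 24.6%. X is not capped, and Appendix 1 says patients often split doses. With extra openings distributed as Poisson with mean 1 a week, the figures fall to 5.1% and 10.0%. With clustered misses (beta-binomial, correlation 0.1 to 0.3) they fall to 8.4-4.9% and 16.2-9.6%.

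**The case against.** The strongest defence is that the composite is an openly broad proxy. The section on measuring diversion says no standard measure exists and presents the monitor as a supplement to self-report and urine testing. Participants are paid to return the device, which is some evidence against giving away a whole pack. The give-away item belongs to the questionnaire being adapted, each behaviour is to be explored individually, and per-protocol analyses are planned among those who start treatment. All of this stands. It confines the gap to the definition of the composite, but it does not change which participants H4 counts.

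A reader might infer from the cut-off table that one lapse is judged differently according to prescribed frequency. The arithmetic does not support that. A missed once-daily opening is a full day's medication, while a missed twice-daily opening is half a day's. A full missed day gives 6/7 = 12/14 = 85.7% and is flagged under both. Dividing by Y treats equal fractions of the prescribed doses equally. What remains is that a once-daily participant has no tolerance.

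A reader might also infer a known bias against O-BMT. Nothing in the documents shows that Y differs by arm, and the control section says the same initiation procedures are followed at the health center. If O-BMT raises prescribing, more of its participants can be flagged for missed doses, but more can also give medication away unscored. These errors pull in opposite directions and there is no basis for netting them.

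**Conclusion.** The main point holds on the text alone: the composite's self-report rule omits a behaviour that its stated purpose includes and its questionnaire covers. The secondary point holds by arithmetic and is minor: one missed once-daily dose in a monitored week counts as diversion for the whole trial. The illustrative flag rates rest entirely on the assumed opening probability and on the other assumptions listed with them.

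The result is misclassification whose net effect on the arm difference has unknown size and direction. It would go too far to say that the composite fails to measure selling or giving away: admitted selling is scored directly, and some giving away is caught by the monitor or urine. Nor is the monitor rule shown to be the reason H4 might fail, since the plan itself concedes low power at margins below 10-14%. The definition should be corrected, because the reported frequency of diversion is a safety result that the plan relies on.

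**What to change.** 1. Define self-reported diversion in the composite as a yes to either the sold item or the item on letting others take the medication, both with the 2-week recall.
2. Keep the monitor and urine components in the primary composite. Pre-specify two sensitivity analyses of H4: the first does not count participants flagged only by the monitor, and the second uses self-report (sold or given) alone. The second is needed because the urine rule is also a non-adherence proxy and remains in the first. Keep everyone in the intention-to-treat denominator.
3. Tabulate monitor-only flags by arm and by prescribed doses per day (Y).

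The cost is one more scored item from a questionnaire already being adapted, a sentence in the outcome definition, and extra analyses and a table from data the plan already collects. The sensitivity analyses are less able to detect covert diversion, so they should stand beside the primary result and not replace it. None of this improves the low power at the 5% margin.
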